#### 9.4.1.2. Primary Analyses

The primary efficacy variable is the change from baseline in total staining score at Day 90.

The primary efficacy analysis will be performed in the ITT population using MMRM. The differences and the intervals will be constructed with the least squares means from the MMRM model with treatment, visit, visit by treatment interaction, and baseline total staining stratum, and baseline total staining stratum by visit interaction as the fixed effects. In order to control the overall type I error rate in the primary efficacy analysis, the sequential procedures will be performed. Under this procedure, the noninferiority will be performed first and the superiority test will be performed next only if the null hypothesis of noninferiority is rejected. To test the hypothesis of noninferiority, a 2-sided 95% confidence interval will be constructed for the difference in the mean change from baseline in total staining at Day 90. If the upper limit of 2-sided CI is less than 2.3 units, then the NATF tear formulation will be considered noninferior to Systane Ultra MD at the 2.3 unit margin. To test the hypothesis of superiority, a 2-sided test for superiority will be performed at the 0.05 significance level.

The primary efficacy variable will also be analyzed similarly on PP population as a sensitivity analysis.

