8.3.2 Primary Efficacy Analysis

The primary efficacy analysis will be performed upon the ITT population using mixed effects repeated measures (MMRM) method. The difference and the 95% confidence interval will be constructed with the least squares means from the MMRM model with

treatment, visit, visit-by-treatment interaction, baseline total staining stratum, and baseline total staining stratum-by-visit interaction as the fixed effects. An unstructured covariance matrix will be selected for the repeated measure covariance.

In order to control the overall type I error rate in the primary efficacy analysis, the sequential procedures will be performed. Under this procedure, the noninferiority test will be performed first and the superiority test will be performed next only if the null hypothesis of noninferiority is rejected. To test the hypothesis of noninferiority, a 2-sided 95% confidence interval (CI) will be constructed for the difference in the mean change from baseline in total staining at Day 90. If the upper limit of 2-sided CI for the treatment difference (011516X minus Systane Ultra MD) is less than 2.3 units, then the 011516X tear formulation will be considered noninferior to Systane Ultra MD. If the upper limit of the aforementioned 2-sided CI is less than 0 units, then the 011516X tear formulation will be considered noninferior to Systane Ultra MD. Details of this procedure will be found in Section 12.0.

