12.0 Overall Type-I Error Control

To control the family-wise type I error rate at 0.05 for multiplicity across the hypothesis tests, a hierarchical gatekeeping procedure will be followed.

Step 1: Test the noninferiority hypothesis. If the upper limit of the 2-sided 95% CI is less than 2.3 units, reject H_0 and go to Step 2. Otherwise stop.

Step 2: Test the superiority hypothesis.

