Appendix D. Changes to Protocol-planned Analyses

There are no changes from the protocol-planned analyses.

Electronic Signatures

User	Date	Justification
	02-Aug-2021 20:44:38 (GMT)	Document Originator Approval
	04-Aug-2021 19:44:44 (GMT)	NC - Study Director Approval
	02-Aug-2021 22:16:07 (GMT)	Subject Matter Expert Approval
	03-Aug-2021 21:36:05 (GMT)	Manager Approval

TITLE PAGE

Protocol 2007-301-005

A Multicenter, Single-masked, Randomized Study to Compare the Efficacy and Safety of a New Artificial Tear Formulation (011516X) with Systane[®] Ultra Multidose for 90 Days in Participants with Dry Eye Disease

PER-PROTOCOL ANALYSES DATA EXCLUSION ALGORITHM

Draft: 06-Aug-2021

Confidentiality Statement

Confidentiality Statement

This document is the property of AbbVie, Inc. and may not, in full or part, be passed on, reproduced, published, distributed to any person, or submitted to any regulatory authority without the express written permission of AbbVie, Inc. AbbVie Optive Super

HISTORY OF CHANGE

Amendment: Not applicable

Date	Description of Change(s)
06-Aug-2021	Initial version (Approved)

2007-301-005 Per-Protocol Analyses Data Exclusion Algorithm

1 Introduction

This document is written to detail the algorithms used to define data exclusions from the per-protocol analysis in the 2007-301-005 Amendment 2 and statistical analysis plan (SAP) Amendment 1.0.

The per-protocol (PP) population is defined in SAP section 4.0. The PP analysis will be implemented on the primary efficacy endpoint only. The PP population will consist of participants who contribute data to the PP analysis after implementing the data exclusion algorithms specified in this document. PP population will come from ITT population who are treated. Data from the participants with a protocol deviation that is deemed to affect primary efficacy assessment from a study visit will be excluded from the PP analysis for that study visit.

2 Algorithms to Define Data Exclusion for PP Analysis

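### SAP 8.3.2 gives its superiority rule (95% CI upper limit below 0) the conclusion noninferior, and Section 12.0 Step 2 does not correct it

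*SAP*

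**What the plan says.** SAP 8.3.2 sets a fixed order in which "the superiority test will be performed next only if the null hypothesis of noninferiority is rejected". The interval is defined once: "To test the hypothesis of noninferiority, a 2-sided 95% confidence interval (CI) will be constructed". Two decision sentences follow.

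- **First rule:** if the upper limit for 011516X minus Systane Ultra MD "is less than 2.3 units, then the 011516X tear formulation will be considered noninferior to Systane Ultra MD".
- **Second rule:** this sentence, also on the upper limit, reads in part "aforementioned 2-sided CI is less than 0 units, then the 011516X tear formulation will be considered noninferior to Systane Ultra MD".

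The section then sends the reader to Section 12.0 for the details. Step 1 there has a criterion ("If the upper limit of the 2-sided 95% CI is less than 2.3 units") and a consequence (reject and go on, or stop). The next line reads in full "Step 2: Test the superiority hypothesis", with no limit, level or conclusion.

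Two other places bear on the meaning. SAP 2.1.2 sets the superiority alternative at a difference below 0. Protocol 9.4.1.2 says: "To test the hypothesis of superiority, a 2-sided test for superiority will be performed at the 0.05 significance level". SAP Appendix D states: "There are no changes from the protocol-planned analyses".

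**The concern.** Two different cut-offs lead to one conclusion. The paragraph promises a superiority test, yet no sentence in it says what result establishes superiority. The sentence with the cut-off of 0 is the only place in either document that ties a confidence limit to the superiority step, and it names the wrong conclusion. The section cited for details leaves the gap open.

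This is the pre-specified decision rule for the primary endpoint. If the trial met the superiority criterion, the report would have to depart from the literal SAP wording to claim it. That invites an avoidable question about whether the claim was pre-specified.

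**Working it through.** **1. Direction.** SAP 8.1 defines change as postbaseline minus baseline, and SAP 8.3.2 takes 011516X minus Systane Ultra MD. A higher staining score is worse, so a negative difference favours 011516X. An upper limit below 0 therefore points to superiority of 011516X.

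**2. The rules side by side.**

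| Source | Criterion | Conclusion stated |
|---|---|---|
| SAP 8.3.2, first rule | upper limit < 2.3 | noninferior |
| SAP 8.3.2, second rule | upper limit < 0 | noninferior |
| SAP 12.0, Step 1 | upper limit < 2.3 | reject, go to Step 2 |
| SAP 12.0, Step 2 | none | none |
| SAP 2.1.2, superiority | alternative: difference < 0 | hypothesis only |
| Protocol 9.4.1.2, superiority | two-sided test at 0.05 | no confidence limit given |

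Upper limit < 0 implies upper limit < 2.3, so the second rule can never change a conclusion reached under the first.

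**3. The plan's own figure.** The nearby computed figure is 170 completers per arm (SAP 2.4: margin 2.3, SD 6.01, true difference 0, one-sided 2.5%, power 90% or greater). The usual formula gives n = 2 x 6.01² x (1.960 + 1.282)² / 2.3² = 143.5, so 144 per arm. With 170 per arm the power is about 94%. The power statement is true, but 170 is not the minimum. Nothing below depends on this; 170 is used only as the planned number of completers.

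**4. When the second rule comes into play.** This is a two-sample t planning approximation; the half-width from the mixed model for repeated measures may differ.

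- 170 per arm: SE = 6.01 x √(2/170) = 0.652; half-width = t(0.975, 338 df) x 0.652 = 1.28.
- 200 per arm: SE = 6.01 x √(2/200) = 0.601; half-width = 1.18.
- SD 5.98 (Protocol 9.2), 170 per arm: half-width 1.28.

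At 170 per arm, the first rule is met when the observed difference is below 2.3 - 1.28 = 1.02, and the second when it is below -1.28 (-1.18 with 200 per arm).

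**5. What the second rule tests.** Probability that the upper limit is below 0, with SD 6.01 and 170 per arm (noncentral t):

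| True difference | Probability |
|---|---|
| 0 (SAP planning assumption) | 0.025 |
| -1 (illustrative assumption) | 0.334 |
| -2 (illustrative assumption) | 0.864 |

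At a true difference of 0 the rule rejects with probability 0.025, which is the favourable side of a two-sided 0.05 test. At a true difference of 2.3, the noninferiority boundary, the probability is about 2 x 10⁻⁸ (normal approximation). The rule is therefore a test of the superiority null in SAP 2.1.2, not of the noninferiority null.

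**The case against.** The strongest reply is that this is a slip of one word with no analytic effect. The sentence is not logically false, because an upper limit below 0 does establish noninferiority; it is redundant and incomplete. The same paragraph names the superiority test as the next step, SAP 2.1.2 gives its hypotheses and direction, and Protocol 9.4.1.2 gives its level. An analyst following Section 12.0 would run the right test. The probabilities above measure how often the sentence becomes relevant, not how often a result would be misreported. Appendix D adds little, since nobody lists a slip as a planned change.

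Most of this stands. The intent can be recovered, the numbers describe relevance rather than damage, and the mismatch with SAP 2.1.2 and Protocol 9.4.1.2 is a missing superiority conclusion, not a rival rule. It does not remove the point. The faulty sentence is the operative rule for the primary endpoint, and no other passage supplies a confidence-limit rule that ends in superiority. A reader should not need to assemble three sections to learn what the primary analysis concludes.

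**Conclusion.** The concern holds. The second decision rule in SAP 8.3.2 has the right cut-off and the wrong conclusion, and Section 12.0 Step 2 does not repair it. It should be fixed, but the harm is limited to labelling: the estimate, interval, type I error, test order, margin and sample size do not change.

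Only results with an upper limit below 0 are touched. That means observed differences below about -1.2 to -1.3, assuming SD 6.01, 170 to 200 per arm and the two-sample approximation. At 170 per arm the chance is 2.5% under the planning assumption of no true difference. It is about 33% and 86% at the illustrative true differences of -1 and -2, which are not from the documents.

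**What to change.** - **SAP 8.3.2:** in the sentence with the cut-off of 0, change *noninferior* to *superior*.
- **SAP 12.0, Step 2:** mirror Step 1, for example: *If the upper limit of the same two-sided 95% CI is below 0, reject H0 and conclude superiority; otherwise conclude noninferiority only.*

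This matches the protocol's two-sided 0.05 test in the favourable direction (one-sided 0.025) and introduces no new rule. The correction belongs in the SAP itself, not at reporting. The cost is one word and one sentence, with no change to the model, alpha, margin or sample size.

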8.3.3 Sensitivity Analyses

Sensitivity analyses will be based on the PP population applying the primary efficacy analytical approaches.

8.4 Secondary Efficacy Analyses

The secondary efficacy variable will be analyzed with the same model described for the primary efficacy analysis in Section 8.3.2. The difference and the 95% CI will be constructed.

8.5 Exploratory Efficacy Analyses

Total staining score other than Day 90, Current Symptom Survey total score (composite of all symptoms) other than Day 90, individual symptom scores from Current Symptom

Survey, corneal staining score, and conjunctival staining score will be analyzed with the same method described for the secondary efficacy analysis in Section 8.3.2.

All other efficacy analyses will be performed to provide descriptive statistics. Summaries of the 011516X and Systane Ultra MD at each scheduled visit will be performed on Schirmer test, TBUT, Functional Vision Questionnaire, and Study Eye Drop Experience and Tolerability Questionnaire.

8.5.1 5-Minute Blurry Vision and Ocular Discomfort Questionnaire

The 5-Minute Blurry Vision and Ocular Discomfort Questionnaire will provide an assessment of blurry vision and ocular discomfort, each on a 0-100 scale. The assessment will be conducted at Day 1 and Day 90/Early Exit. At each visit, measurements will be collected before instillation of one drop to each eye (Baseline), and at post dose time points of 30 seconds, 1 minute, 90 seconds, 2 minutes, 3 minutes, 4 minutes, and 5 minutes. Change from baseline is calculated for each time point minus the pre-dose score of the same day.

8.6 Efficacy Subgroup Analyses

The primary efficacy variable will be analyzed by the stratification factor, Day 1 (Baseline) total ocular staining score in the study eye:

- mild/moderate = total ocular staining score of 6 to 25, and
- severe = total ocular staining score of 26 to 43.

9.0 Safety Analyses

9.1 General Considerations

The following are the general considerations for safety analyses:

- Safety analyses will be performed based on the safety population by treatment group.
- Baseline for safety endpoints is defined as the last non-missing assessment prior to the first dose of the single-blind treatment.
- Continuous variables will be summarized by number of participants with observed values (n), mean, standard deviation (SD), median, 1st and 3rd quartiles (Q1, Q3), minimum (min), and maximum (max).
- Categorical variables will be summarized by number of participants with observed values or events and percentages based on the specified population.
- AEs will be coded using MedDRA version 23.0 or higher.

9.2 Adverse Events

An AE is any untoward medical occurrence in a patient or clinical study participant, temporally associated with the use of study treatment, whether or not considered related to the study treatment.

An AE can therefore be any unfavorable and unintended sign (including an abnormal laboratory finding), symptom, or disease (new or exacerbated) temporally associated with the use of study treatment.

9.2.1 Treatment-emergent Adverse Events

An AE will be considered a TEAE if the AE began or worsened (increased in severity or became serious) on or after the date (and time, if known) of the first dose of randomized study treatment. However, an AE that occurs more than 30 days after the last dose of randomized study treatment for participants will not be counted as a TEAE.

An AE will be considered a treatment-emergent serious AE (TESAE) if it is a TEAE that additionally meets any SAE criterion.

9.2.2 Adverse Event Overview

Overall summary of TEAEs will be provided on a per-participant level for TEAEs, treatment-related TEAEs, TESAEs, deaths, and TEAEs leading to study treatment discontinuation.

9.2.3 Treatment-emergent Adverse Events by SOC and/or PT

The number and percentage of participants with TEAEs will be tabulated by primary system organ class (SOC) and preferred term (PT).

The number and percentage of participants with TEAEs will be tabulated by primary SOC, preferred term, and severity. If more than one event is coded to the same preferred term for the same participant, the participant will be counted only once for that preferred term using the greatest severity for the summarization by severity. If the severity of a TEAE is missing, the maximum severity will be assigned to the event for the summarization by severity. The value will be displayed as missing in the data listing.

The number and percentage of participants with treatment-related TEAEs will be tabulated by primary SOC and preferred term; and by primary SOC, preferred term, and relationship. If the relationship to the treatment is missing for a TEAE, the event will be considered related to the treatment for the summarization. The value will be displayed as missing in the data listing.

Ocular treatment-emergent AEs will also be summarized. An ocular TEAE will be defined by the location information on the adverse event page in the eCRF. Ocular treatment-emergent AEs will be summarized overall by treatment group and preferred term.

The incidence of common ($\geq 2\%$ [after rounding] of participants in any treatment group) TEAEs will be summarized by preferred term and treatment group.

Summary tables will be provided for TEAEs leading to treatment discontinuation and TESAEs if they occurred in 5 or more participants.

9.2.4 SAEs, Deaths and Adverse Events Leading to Study Drug Discontinuation

SAEs, deaths and AEs leading to study drug discontinuation will be tabulated by primary SOC.

9.2.5 Adverse Events of Special Interest

There are no protocol-specified adverse events of special interest for this study.

9.3 Analysis of Laboratory Data

9.3.1 Urine Pregnancy Test

Women of childbearing potential will have urine pregnancy tests performed at the Screening (Day -7) and Day 90/Early Exit visits. At each visit, the investigator should discuss contraceptive use compliance with WOCBP. Positive test results for females of childbearing potential will be listed.

9.3.2 Clinical Laboratory Parameters

Clinical laboratory parameters are not evaluated in this study.

9.4 Analysis of Vital Signs

Vital sign parameters are not evaluated in this study.

9.5 Other Safety Analyses

9.5.1 Biomicroscopy

Biomicroscopy will be performed in each eye at each visit, by slit lamp examination, without pupil dilation, including but not limited to lids/lashes, conjunctiva, cornea and

anterior chamber. Observations for the examination will be graded on a 5-point scale (0=none, 0.5=trace, 1=mild, 2=moderate, 3=severe) except for the anterior chamber (in cells: 0=0 cells, +0.5=1-5 cells, +1=6-15 cells, +2=16-25 cells, +3=26-50 cells, and +4=>50 cells; in flare: 0=None, +1=faint, +2=moderate, +3= marked and +4=intense).

The number and percent of patients with clinically significant biomicroscopy findings at one or more visits will be tabulated. A clinically significant finding is defined as more than one severity grade increase (worsening) from baseline. If a pathology is recorded at a follow-up visit but not at baseline, the baseline will be imputed with the same pathology, with a grade of zero (none).

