## **5.2.** Exclusion Criteria

Participants are excluded from the study if any of the following criteria apply:

1.	Medical Conditions		
1.01	Have uncontrolled severe systemic disease that, in the assessment of the investigator, would put safety of the participant at risk through participation, or which would prevent or confound protocol-specified assessments (eg, hypertension and diabetes, Sjögren's syndrome, rheumatoid arthritis, systemic lupus erythematosus, immunodeficiency disease, etc.)		
1.02	At the Screening (Day -7) or Baseline (Day 1) visits, either eye has		
	• Corneal staining score of 5 in any of the 5 zones or a total score of > 19 based on the modified NEI grading scheme (score range = 0 to 5; graded in 5 zones of the cornea for a total score range of 0 to 25)		
	or		
	• Conjunctival staining score of 5 in any of the 6 zones based on the modified NEI grading scheme (score range = 0 to 5 per zone)		
1.03	Participant has worn contact lenses in the last 90 days prior to the Screening (Day -7) visit and/or participant anticipates contact lens wear during the study		
1.04	Have any scheduled or planned systemic surgery or procedure during the study, which in the investigator's opinion, may impact the participant's study participation		

1.05	Presence of 1 or more of the following ocular conditions:			
	Active ocular infection or non-keratoconjunctivitis sicca (KCS) ocular inflammation			
	Active ocular allergy			
	History of recurrent herpes keratitis or active disease within 6 months prior to the Screening (Day -7) visit			
	Corneal disorder or abnormality that affects corneal sensitivity or normal spreading of the tear film (except superficial punctate keratitis)			
	• Severe blepharitis or obvious inflammation of the lid margin, which in the judgment of the investigator, may interfere with the interpretation of the study results			
	Keratoconjunctivitis sicca secondary to the destruction of conjunctival goblet cells, such as occurs with vitamin A deficiency or scarring such as that with cicatricial pemphigoid, alkali burns, Stevens-Johnson syndrome, trachoma, or irradiation			
	Substantial non-KCS keratitis with overlying corneal stain or other significant corneal findings not directly related to DED; in addition, participants with DED signs/symptoms (eg, filamentary keratitis) of a severity where topical monotherapy with an artificial tear would be inappropriate			
2.	Prior/Concomitant Therapy			

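### SAP 9.5.1: a lid, conjunctival or corneal sign graded moderate at baseline can never meet the biomicroscopy criterion, and the unit in which a grade is counted is not defined

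*SAP*

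**What the plan says.** SAP 9.5.1 sets the scale: "Observations for the examination will be graded on a 5-point scale (0=none, 0.5=trace, 1=mild, 2=moderate, 3=severe) except for the anterior chamber". The anterior chamber has its own scales, "in cells: 0=0 cells, +0.5=1-5 cells, +1=6-15 cells, +2=16-25 cells, +3=26-50 cells, and +4=>50 cells" and "in flare: 0=None, +1=faint, +2=moderate, +3= marked and +4=intense".

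The output is described as follows: "The number and percent of patients with clinically significant biomicroscopy findings at one or more visits will be tabulated". The threshold is: "A clinically significant finding is defined as more than one severity grade increase (worsening) from baseline". A pathology recorded at follow-up but not at baseline is given a baseline grade of zero.

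Protocol 8.2.3 and SAP Appendix B list the same grades. Neither says how a change between grades is to be counted. Protocol 9.4.3 promises only descriptive statistics for the other safety variables.

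On entry, Protocol 5.2, criterion 1.05, lists ocular conditions that exclude a participant, among them "Severe blepharitis or obvious inflammation of the lid margin, which in the judgment of the investigator" may interfere with interpretation of the results. The criterion sets no upper limit in biomicroscopy grades.

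**The concern.** Two features of the rule interact badly with this scale.

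- **Ceiling.** The threshold is strictly more than one grade and the top grade is 3. A sign that starts at 2 has only one grade of room, so its worsening to severe falls outside the definition.
- **Undefined unit.** The codes are unevenly spaced: two half-unit intervals, then two whole-unit intervals. Counting numeric units and counting category steps therefore give different answers for none-to-mild. The zero-baseline imputation makes this more than a corner case, because every newly recorded mild finding on these signs is a change from 0 to 1.

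Two programmers could therefore report different percentages from the same data. On the step reading, the table would call a change from none to mild clinically significant and a change from moderate to severe not.

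**Working it through.** The plan states no figure to reproduce. The check lists every possible worsening on each scale in SAP 9.5.1 and tests it against the threshold under two readings:

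- **Units:** follow-up code minus baseline code is greater than 1.
- **Steps:** the number of categories moved is greater than 1.

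Lid, conjunctival and corneal signs use the codes 0, 0.5, 1, 2, 3. Five categories give 5 × 4 / 2 = 10 possible worsenings:

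| Change | Units | Steps | Counted by units | Counted by steps |
|---|---|---|---|---|
| 0 to 0.5 | 0.5 | 1 | no | no |
| 0 to 1 | 1 | 2 | no | **yes** |
| 0 to 2 | 2 | 3 | yes | yes |
| 0 to 3 | 3 | 4 | yes | yes |
| 0.5 to 1 | 0.5 | 1 | no | no |
| 0.5 to 2 | 1.5 | 2 | yes | yes |
| 0.5 to 3 | 2.5 | 3 | yes | yes |
| 1 to 2 | 1 | 1 | no | no |
| 1 to 3 | 2 | 2 | yes | yes |
| 2 to 3 | 1 | 1 | **no** | **no** |
| Total counted | | | 5 of 10 | 6 of 10 |

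Four results follow.

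1. From baseline 2 the only worsening is 2 to 3. It is not counted on either reading, so the criterion cannot be met for that sign.
2. Four changes end in severe (from 0, 0.5, 1 and 2). Three are counted on both readings, and the one from moderate on neither.
3. The readings differ in one change only, 0 to 1.
4. Mild-to-moderate (1 to 2) is not counted on either reading.

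For the anterior chamber:

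- **Cells** (0, 0.5, 1, 2, 3, 4): 6 × 5 / 2 = 15 worsenings, of which 9 count by units and 10 by steps. The difference is again 0 to 1.
- **Flare** (0, 1, 2, 3, 4): 10 worsenings, of which 6 count on both readings.
- On both scales, 2 to 4 is two units and two steps, so it counts. A grade of 2 at baseline is not a dead end there.

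**The case against.** The strongest reply is that the arithmetic is right but reaches less far than it seems. Four stronger conclusions are tempting, and the documents support none of them.

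- **That an eye starting at moderate can never qualify.** The imputation rule compares each pathology with its own baseline, so the criterion works sign by sign. An eye with moderate hyperemia still qualifies if lid edema goes from 0 to 2, or cells from 0 to 2. Cells and flare can also rise from 2 to 4. The ceiling belongs to the individual lid, conjunctival or corneal sign.
- **That this is the only biomicroscopy analysis planned.** SAP 1.0 places the table and listing specifications in a separate document that is not available here. One can say only that SAP 9.5.1 names no shift table or worst-grade table.
- **That moderate-to-severe worsening would go unseen.** Protocol Appendix 2 treats greater intensity of a pre-existing condition as an adverse event, SAP 9.2.1 counts worsening as treatment-emergent, and SAP 9.2.3 summarizes ocular events separately. This is a real backstop but a partial one: nothing requires a rise in slit-lamp grade to be recorded as an adverse event, so capture depends on the investigator.
- **That many participants are affected.** No document gives the frequency of moderate findings at baseline. Criterion 1.05 may also remove some of them, such as obvious lid-margin inflammation judged to interfere, or significant corneal findings unrelated to dry eye. Moderate hyperemia is the most plausible remaining case.

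It can also be said that the threshold is a design choice for the sponsor. That is fair as to where the cutoff lies. It does not answer the missing definition of a grade, or explain why a rise to severe should count from mild but not from moderate.

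**Conclusion.** The point holds in its limited form. For lid erythema and edema, conjunctival hyperemia and edema, and corneal edema, a baseline grade of moderate makes the criterion unreachable for that sign on either reading. Separately, the reported percentage depends on an unstated choice for none-to-mild changes: 6 or 5 of the 10 possible worsenings on these signs, and 10 or 9 of 15 for cells.

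These are counts of possible changes, each given equal weight. They are not estimates of participants, and the documents do not allow a conversion. The conclusion rests on reading the threshold literally, as strictly more than one, and on comparing each sign with its own baseline.

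Severity is minor. The output is one descriptive safety table, and no hypothesis test or error rate depends on it. It is worth correcting because the correction is cheap.

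**What to change.** In SAP 9.5.1:

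1. State whether a grade means one unit of the numeric code or one category step, and how trace (0.5) counts.
2. Make worsening to severe visible in one of two ways:
   - also count any increase to grade 3 on the signs graded 0 to 3, which raises the worsenings counted to 5 + 1 = 6 of 10 by units or 6 + 1 = 7 of 10 by steps; or
   - add a shift table from baseline grade to worst postbaseline grade for each sign, by treatment group.

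The first option still leaves mild-to-moderate uncounted. The shift table shows every change to the worst grade, including that one, without choosing a threshold. Any cutoff for cells and flare should be left to the sponsor, since the documents give no basis for a different one. The zero-baseline imputation can stay.

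The cost is a sentence or two in the SAP and either one more descriptive table or a somewhat higher number of participants reported with a finding. No new data are needed.
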